6.8 CALCULATION OF TIME TO EVENT

This section describes the calculation of the time to event and the time that patients without an event are in the study (under risk).

Consistent with that approach, the respective time intervals determine the start and end for the derivation of occurrence of a specific event.

For those patients with an event, the time to event is calculated as:

<date of event> - < start date> + 1

For those patients without an event, the time at risk is calculated as:

<date of censoring> - < start date > + 1

6.8.1 Start date

In general, the time to event will be derived from the date of randomisation.

For the following endpoints (analysed as occurrence or time to first event), the date of first drug intake will be used as the start date:

- AE analyses according to [Section 7.8.1](#)
- Endpoints purely based on laboratory measurements or concomitant medications, that include a relation to baseline (such as decrease from baseline $\geq 40\%$, doubling vs baseline, etc.)

Please note, that for composite endpoints, that include component(s) using randomisation date and other component(s) using first drug intake date as start date, the time at risk for the composite will start with date of randomisation (which may be earlier). For the individual components, the component specific start date will be used.

6.8.2 Date of event

For time-to-death endpoints, the respective death date will be used rather than time to the first onset of the fatal AE.

For composite outcomes, e.g. time to first occurrence of cardiovascular (CV) death or HFE until end of trial visit, the earliest onset date of the corresponding components will be used.

The time to first occurrence type of endpoints based on laboratory data including endpoints which have the requirement of a “sustained” measurement are determined by the date of the first measurement that fulfils this condition.

For events with multiple possible episodes, such as HFE or all-cause hospitalisation, the admission date of the first hospitalisation will be used, unless noted otherwise. The same applies to time-to-AE analysis, where the onset date of the first episode will be used.

6.8.3 Censoring

The underlying principle is that the censoring date should be the last date a patient was known to be free of an endpoint event (e.g. free of each component of CV death and HFE).

For all endpoints except all-cause mortality and cause-specific death, patients without occurrence of a specific endpoint (composite endpoint or individual components) will be considered censored at the individual day of end-of-study.

The individual day of trial completion will be the latest of:

- last onset of an AE or date of death
- onset dates of adjudicated events
- end of treatment
- last visit date (NYHA class, KCCQ, pregnancy test, vital signs, ECG, or central laboratory)

Censoring is considered independent from study drug intake.

All-cause mortality

A patient without the event will be censored at the latest of:

- individual day of trial completion (without the restrictions defined above for patients with withdrawn consent or lost to follow-up)
- last date known alive from the vital status page

Endpoints of any cause-specific death, e.g. CV death

The same censoring rule as for all-cause mortality applies, and in addition, date of death if died from other causes than the one specified in the endpoint.

Endpoints based on laboratory data only

Patients who already fulfil the respective condition at baseline are not considered in the number of patients at risk for this endpoint.

If a baseline laboratory measurement is not available for the parameter of interest, it is assumed that the patient did not experience the condition corresponding to the endpoint at baseline and the patient is included in the patients at risk for this endpoint. Patients without an event and available post-baseline laboratory measurement will be considered censored at the date of last laboratory sampling of the corresponding parameter. Patients with a missing baseline laboratory value required to derive a change from baseline and patients without laboratory data following the baseline measurement will be censored on the date of randomisation.

Composite endpoints (analysed using a time-to-event approach)

Only patients that are included in the analyses for all components of the composite endpoint will be included in the analysis of the composite.

Of those, a patient with at least one event in any of the components of the composite will be considered to have an event and the date of the first event will be used for the composite endpoint. A patient without an event will be considered censored at the earliest of all censoring dates of the component endpoints.

7. PLANNED ANALYSIS

For End-Of-Text (EoT) tables, the set of summary statistics is: N / Mean / Standard Deviation (SD) / Standard Error (SE) / Minimum (Min) / lower quartile (Q1) / Median / upper quartile (Q3) / Maximum (Max). The 1st and 99th percentiles might be substituting minimum and maximum in tables with open-ended values to safeguard against implausible extremes.

Geometric means and ranges will be added to the presentation or replace the presentation of mean and standard deviation for parameters that follow a log-normal distribution rather than a normal distribution.

Statistical parameters will be displayed to a defined number of decimal places as specified in the BI guideline “Standards for Reporting of Clinical Trials and Project Summaries” (3)

Tabulations of frequencies for categorical data will include all possible categories and will display the number of observations in a category as well as the percentage (%) relative to the respective treatment group (unless otherwise specified, all patients in the respective patient set whether they have non-missing values or not). Percentages will be rounded to one decimal place. The category missing will be displayed only if there are actually missing values.

Disposition of the patient population participating in the trial will be analysed by treatment groups, and stratum and presented in the clinical trial report as a frequency-distribution.

Disposition as required for reporting for the trial in European Clinical Trials Database (EudraCT) will be provided. Enrolment will be summarised by country and by age group for reporting in EudraCT.

The reason for not randomising screened patients will be summarized descriptively.

The frequency of patients with iPDs will be presented by treatment group for the randomised set (RS). The frequency of patients in different analysis sets will also be presented for each treatment group.

Descriptive statistics on the impact of COVID-19 on study visits as well as study medication intake will be provided.

7.1 DEMOGRAPHIC AND OTHER BASELINE CHARACTERISTICS

Demographics and baseline characteristics will be analysed based on the RS. Demographics will be repeated on the TS if the analysis sets differ by more than 1%. Standard descriptive analysis and summary tables will be presented.

Descriptive analysis of the following variables measured at baseline will be presented: Age, BMI, time since diagnosis, systolic blood pressure (SBP), diastolic blood pressure (DBP), heart rate, weight, eGFR, NT-proBNP, LVEF, KCCQ-TSS and hematocrit.

A summary of the number of patients in each randomisation stratum (de novo or decompensated chronic HF) per treatment will also be shown. The information will be based upon the data received from the IRT provider.

7.2 CONCOMITANT DISEASES AND MEDICATION

Only descriptive statistics are planned for this section of the report using the RS. Concomitant medication use will be summarised by Anatomical-Therapeutic-Chemical classification level 3 (ATC3) and preferred name. Summaries will be presented for concomitant therapies taken before initial hospitalisation, taken at baseline and separately for concomitant medications. Separate summaries of use of heart failure-related drugs (e.g. ARNi, beta-blockers, ivabradine, diuretics, ACE-inhibitors, ARBs, MRAs, cardiac glycosides), anticoagulants, acetylsalicylic acid (ASA), or lipid lowering drugs will be presented. Use of devices and other non-medication therapy taken before initial hospitalisation and separately for those newly introduced after initial hospitalisation will also be summarised.

Concomitant diseases will be summarised by system organ class and preferred term. Relevant medical history by treatment group will also be presented.

7.3 TREATMENT COMPLIANCE

Only descriptive statistics are planned for this section of the report. The number and percentage of patients with overall compliance will be reported. Overall compliance will be calculated as a weighted average of reported compliance. The sum of all reported compliance over the planned visits will be divided by the total duration. The TS will be considered.

7.4 PRIMARY ENDPOINT

The efficacy analysis will be based on the RS, including all randomised patients. Analyses will be performed according to the intention-to-treat principle, with the use of all available data (on and off-treatment) through the trial period. This equates to a treatment-policy style estimand. Treatment will be evaluated as randomised.

The primary endpoint is clinical benefit (4 and 5) assessed using a stratified win ratio approach. The statistical model will be a non-parametric generalised pairwise comparison within HF status strata. The variance of the stratified win ratio will be calculated using the asymptotic normal U statistics approach (5).

Superiority of empagliflozin vs. placebo will be evaluated with one-sided tests, at a significance level of 0.025.

7.4.1 Primary analysis of the primary endpoint

The primary endpoint is clinical benefit, a composite of death, number of HFEs, time to first HFE and change from baseline in KCCQ-TSS after 90 days of treatment. This will be assessed using a stratified win ratio approach.

All patients randomised to empagliflozin are compared to all patients randomised to placebo within their stratum.

For any two patients, a patient will win, i.e. achieve a better clinical outcome, as determined by assessing the following criteria sequentially, stopping when an advantage for either patient is shown:

1. Death within common follow-up time
 - death is worse than no death
 - earlier death is worse
 - tied, if not possible to determine
2. Number of HFEs within common follow-up time
 - more HFEs is worse
 - tied, if same number of HFEs
3. Time to first HFE within common follow-up time
 - earlier HFE is worse
 - tied, if not possible to determine
4. KCCQ-TSS change from baseline at Day 90
 - more positive change from baseline is better
 - the threshold for the difference is ≥ 5 for a win
 - tied, if difference < 5

Note, priority is therefore given to death over HFE, and both of these over changes in KCCQ-TSS. Below are some examples:

1. Death, e.g.:
 - Patient A dies 30 days after randomisation (loses)
 - Patient B dies 40 days after randomisation (wins)
2. If no winner based on death, number of HFEs within common follow-up time, e.g.:
 - Patient A had two HFEs (loses)
 - Patient B had one HFE (wins)
3. If no winner based on number of HFEs, time to first HFE, e.g.:
 - Patient A had an HFE 30 days after randomisation (loses)
 - Patient B had an HFE 50 days after randomisation (wins)

4. If no winner based on time to first HFE, KCCQ-TSS change from baseline at Day 90, e.g.:
 - Patient A: KCCQ-TSS change from baseline at Day 90 is 5 (loses)
 - Patient B: KCCQ-TSS change from baseline at Day 90 is 11 (wins)

The implemented generalised pairwise comparisons approach compares all patients in one treatment group to all other patients within their strata in the other treatment group. The stratified win ratio is then calculated as the total number of wins in the empagliflozin group across all strata divided by the total number of losses.

Applying weights that are analogous to a Mantel-Haenszel approach ([10](#)), the stratified win ratio is:

$$WR = \frac{\sum_{m=1}^2 n_e^{(m)} / N^{(m)}}{\sum_{m=1}^2 n_p^{(m)} / N^{(m)}}$$

where m is the stratum number ($m = 1, 2$), $n_e^{(m)}$ is the number of wins in the empagliflozin group in the m^{th} stratum, $n_p^{(m)}$ is the number of wins in the placebo group in the m^{th} stratum and $N^{(m)}$ is the total number of patients in the m^{th} stratum.

The variance is calculated by the asymptotic normal U statistic approach ([5](#))

Separate summaries for each component of this endpoint will also be presented.

The method of handling missing KCCQ-TSS values for this analysis is described in [Section 6.6.1](#).

7.5 SECONDARY ENDPOINTS

7.5.1 Key secondary endpoint

This section is not applicable, as no key secondary endpoint has been specified in the protocol.

7.5.2 Secondary endpoints

Other secondary endpoints are exploratory. No correction for multiple hypotheses testing will be made.

Change from baseline in continuous endpoints, such as KCCQ-TSS, will be analysed using restricted maximum likelihood estimation based on a mixed-effect model for repeated measures (MMRM) analysis to obtain adjusted means for the treatment effects. This model will include discrete fixed effects for treatment group (empagliflozin or placebo) and HF status (de novo or decompensated chronic HF) at each visit and continuous fixed effects for baseline value at each visit. Missing data caused by patient withdrawal or other reasons will be handled implicitly by the MMRM approach. An unstructured covariance structure will be used to model the within-patient errors.

Area under the curve (AUC) of change from baseline in log-transformed NT-proBNP level over 30 days of treatment will be analysed by an analysis of covariance (ANCOVA). Based on literature reviews, NT-proBNP level is regarded as log-normally distributed, therefore values will be log-transformed prior to analysis (6). The linear trapezoidal rule will be used to calculate the AUC after the log-transformation has been applied to each value.

ANCOVA with a discrete fixed effect for HF status (de novo or decompensated chronic HF) and a continuous fixed effect for baseline NT-proBNP level (log-transformed) will be used to compare treatment groups. The method of handling missing NT-proBNP levels for this analysis is described in [Section 6.6.1](#).

Comparisons between treatment groups regarding the binary endpoint variable (improvement in KCCQ-TSS of ≥ 10 points after 90 days of treatment) will be performed using a logistic regression model adjusting for the binary covariate HF status (de novo or decompensated chronic HF) and continuous covariate baseline KCCQ-TSS score. The likelihood-ratio test will be used to test for a difference between treatments. Adjusted odds ratios together with 1-sided 97.5% confidence limits will be used to quantify the effect of treatment, comparing empagliflozin to placebo as the reference.

Time to event endpoints will be analysed using the Cox proportional hazards model (7) with HF status (de novo or decompensated chronic HF) as a covariate. Hazard ratios (HRs) and their associated one-sided 97.5% confidence limits will be estimated for evaluating the superiority of empagliflozin to placebo. All time-to-event endpoints will be reported in days.

Other secondary endpoints will be summarised descriptively [including days alive and out of hospital (DAOH)]. DAOH will be summarised as a percentage (12).

The follow-up time for DAOH analyses is defined as the minimum of 90 days after randomisation, or time between randomisation and date of censoring for non-fatal events except for patients who died within the first 90 days, where 90 days is considered as the DAOH follow-up time. Days alive and out of hospital (DAOH) for each patient is calculated as follow-up time subtracted by the number of days in hospital during the 90 days after randomisation as well as the number of days being dead within the first 90 days. Percentage DAOH is defined as DAOH divided by the DAOH follow-up time of each patient multiplied by 100.

Additionally, a negative binomial model (including HF status [de novo or decompensated chronic HF] as a factor) will be fitted to the data of recurrent HFE. The rate ratio and confidence interval will be reported.

The endpoints “diuretic effect as assessed by weight loss per mean daily loop diuretic dose after 15 days of treatment” and “diuretic effect as assessed by weight loss per mean daily loop diuretic dose after 30 days of treatment” will be defined as follows:

$$\frac{\text{Change in weight (kg) from baseline to Day T}}{\frac{\text{Mean daily i. v. dose}}{40 \text{ mg}} \text{ or } \frac{\text{mean daily oral dose}}{80 \text{ mg}} \text{ furosemide\# up to Day T}}$$

or equivalent loop diuretic dose

where the mean daily dose is defined as:

$$\frac{\sum_{x=1}^X N_x x d_x}{T}$$

and N = number of days on dose level x, d = dose level and T = day of the weight measurement.

The equivalent loop diuretic dose to a single dose of 40 mg of furosemide is defined as 20 mg of torasemide or 1 mg of bumetanide.

The dose level will be counted as 0 mg, if patients do not take loop diuretics for part of the time period. Patients not taking loop diuretics at all will be excluded from the calculation. Missing data will be handled according to the rules set out in [Section 6.6.2](#).

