### **7.1 NULL AND ALTERNATIVE HYPOTHESES**

For the primary endpoint, superiority of empagliflozin vs. placebo will be evaluated with one-sided tests, at a significance level of 0.025, in the following structure:

Null hypothesis – There is no difference between the effect of placebo and the effect of empagliflozin or the effect of placebo is greater.

Alternative hypothesis – The effect of empagliflozin is greater than the effect of placebo.

Secondary and further endpoints will be evaluated in an exploratory manner.

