### **7.2 PLANNED ANALYSES**

#### **7.2.1 General considerations**

The efficacy analysis will be based on the randomised set (RS), including all randomised patients. Analyses will be performed according to the intention-to-treat principle, with the use of all available data (on and off-treatment) through the trial period. This equates to a treatment-policy style estimand.

If a Per Protocol Set (PPS) is required, this will also be specified in the TSAP. Important protocol deviations will be described in the TSAP.

The safety analysis will be based on the treated set (TS), which consists of all patients treated with at least one dose of trial medication.

For both efficacy and safety analyses, treatment will be evaluated as randomised.

For all endpoints, baseline will be defined as the last available measurement before start of trial medication.

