### **7.3            HANDLING OF MISSING DATA**

Missing data for KCCQ-TSS and NT-proBNP will be estimated using multiple imputation, according to whether patients are on-treatment or off-treatment.

Further details on multiple imputation and rules for handling missing data for other secondary and further endpoints will be specified in the TSAP.

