### **7.4            RANDOMISATION**

The trial will be performed as a double-blind design with respect to placebo and empagliflozin. Patients will be randomised to the trial treatments in a 1:1 ratio. Patients will be stratified by HF status (de novo or decompensated chronic HF).

Patients will be randomised in blocks to double-blind treatment via an IRT system.

Approximately equal numbers of patients will be randomised to each treatment group.

BI will arrange for the randomisation and the packaging and labelling of trial medication. The randomisation list will be generated using a validated system, which involves a pseudo-random number generator so that the resulting treatment will be both reproducible and non-predictable. The block size will be documented in the Clinical Trial Report. Access to the codes will be controlled and documented.

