### **7.5            DETERMINATION OF SAMPLE SIZE**

Powers for superiority in were estimated by simulation using a shared frailty approach. Initially a frailty value was simulated for each patient using a gamma distribution. Deaths were assumed to have constant hazard for any given patient dependent upon the frailty term, leading to a marginal Lomax distribution. HFEs were assumed to have a Poisson distribution within patients, again depending on the frailty parameter, leading to a marginal negative binomial distribution. The number of HFEs per patient was nominally capped at 7 per patient over the 90 day period. For KCCQ-TSS, the frailty terms were directly transformed into a capped normal distribution (values below 0 or above 100 set to 0 and 100 respectively). High frailties corresponded to low KCCQ-TSS scores and vice versa. The use of a shared frailty

parameter ensures correlation between components of the primary endpoint so that patients with poor outcomes in one component are also more likely to have a poor outcome in the others. Ten thousand simulations were used for each scenario. Calculations of the win ratio were performed using the generalised pairwise comparisons method from [Section 7.2.2](#). Simulations and calculations were performed using R statistical software Version 3.5.1.

A sample size of 500 randomised patients in total (250 per treatment group) would provide 87.4% power to detect a difference between the empagliflozin treatment group and placebo treatment group, in the win ratio, at a one-sided significance level of 0.025, assuming the following:

Proportion of patients who die within 90 days = 5% [[R19-2932](#)]

Hazard ratio for death component = 0.8 [[P15-09840](#)]

Proportion of patients with at least one HFE within 90 days = 15% [[R19-2932](#)]

Hazard ratio for HFE component = 0.7 [[P15-09840](#)]

KCCQ-TSS placebo mean = 55 [[R17-3082](#)]

KCCQ-TSS baseline adjusted standard deviation = 20 [[R17-3097](#)]

KCCQ-TSS treatment effect = 6 [[R19-3124](#)]

KCCQ-TSS win threshold = 5 [[R17-2687](#)]

Table 7.5: 1

Power estimates for various combinations of KCCQ-TSS treatment effects and death/HFE hazard ratios with 500 patients in total

HR for death	HR for HFE	KCCQ-TSS treatment effect			
		4	5	6	7
0.7	0.7	66.9%	80.1%	89.4%	94.7%
0.8	0.7	63.6%	77.2%	87.4%	93.4%
0.8	0.8	54.6%	68.8%	81.3%	89.7%

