For KCCQ-TSS, the stratified win ratio will be calculated using these imputed data sets, by combining with the non-imputed death and HFE data. Because the stratified win ratio is log-normally distributed ([10](#)), Rubin's rules ([13](#)) can be used on the log-transformed win ratios to combine treatment estimates across the 100 imputations.

The implicit assumption underlying the imputations and analyses is that unobserved off treatment patient measurements will lose any treatment effect immediately post-treatment discontinuation.

A more technical description of the method can be found in [Appendix 9.2](#).

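### The KCCQ-TSS change analysis treats missing scores as missing at random whatever the treatment status, while the primary endpoint's symptom tier removes the drug effect from unobserved off-treatment scores; the two should be aligned or reported side by side

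*SAP*

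**What the plan says.** - **Estimand.** Protocol 7.2.1 bases the efficacy analysis on all randomised patients and on all data collected on or off treatment, and adds: "This equates to a treatment-policy style estimand". The sentence is not confined to the primary endpoint.
- **General missing-data rule.** Protocol 7.3: "Missing data for KCCQ-TSS and NT-proBNP will be estimated using multiple imputation, according to whether patients are on-treatment or off-treatment". It leaves the rules for other secondary and further endpoints to the SAP.
- **KCCQ-TSS change.** SAP 7.5.2 specifies an MMRM with treatment, HF status and baseline, each by visit, and an unstructured covariance. On missing data it says: "Missing data caused by patient withdrawal or other reasons will be handled implicitly by the MMRM approach". Protocol 7.2.3 contains the same sentence.
- **KCCQ-TSS in the win ratio, and NT-proBNP.** SAP 6.6.1 and Appendix 9.2 impute missing on-treatment values as missing at random and missing off-treatment values by jump-to-placebo, with 100 imputations combined by Rubin's rules. The stated premise is that "unobserved off treatment patient measurements will lose any treatment effect immediately post-treatment discontinuation". For KCCQ-TSS, the SAP confines this imputation to the win ratio.
- **Status.** Protocol 7.1 and SAP 7.5.2 make all secondary endpoints exploratory.

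**The concern.** An empagliflozin patient who stops drug and has no Day-90 score is handled in two ways. In tier 4 of the win ratio the unobserved score carries no drug effect. In the MMRM it is predicted from the patient's earlier scores and from the observed empagliflozin patients, most of whom will be on drug, so it can carry up to the full effect.

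The plan foresees such patients. Under Protocol 3.3.4.1 a stopper who cannot attend may be followed by phone or, at the minimum, for vital status and HFEs only. Under 3.3.4.2, data collection ends when consent is withdrawn. Missing Day-90 scores will therefore tend to fall among patients off drug.

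The MMRM gives the KCCQ-TSS effect in points, the natural figure for interpreting the symptom tier. If the two analyses rest on opposite premises for the same scores, the points estimate cannot be read directly against the tier-4 result, and any bias from the difference does not show in its confidence interval.

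**Working it through.** **1. The plan's own figure.** There is no power or precision figure for the MMRM. The only one is for the win ratio: "A sample size of 500 randomised patients in total (250 per treatment group) would provide 87.4% power", at one-sided 0.025. Simulating the model of Protocol 7.5 gave 88.3% with a frailty variance of 0.05, 83.9% with 0.5 and 84.7% with 10. The protocol does not state that variance, so 87.4% is attainable but cannot be confirmed. Nothing below depends on it.

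**2. Inputs.** From Protocol 7.5: "KCCQ-TSS treatment effect = 6", baseline-adjusted SD 20, 250 per arm. Not in the documents, so assumed: m, the share of empagliflozin patients off drug with no Day-90 score, from 5% to 15%; and a between-visit correlation of 0.6.

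**3. Upper bound.** Suppose the SAP 6.6.1 premise is true and scores are otherwise missing at random.

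- True treatment-policy difference, with all stoppers' Day-90 scores unobserved: 6 × (1 − m).
- MMRM difference when the stoppers have no off-drug scores at all: 6.
- Excess: 6 − 6 × (1 − m) = 6m.

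| m | Difference under loss of effect | MMRM | Excess |
|---|---|---|---|
| 5% | 5.70 | 6.00 | 0.30 |
| 10% | 5.40 | 6.00 | 0.60 |
| 15% | 5.10 | 6.00 | 0.90 |

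**4. Why this is a bound.** Protocol 7.2.1 brings observed off-drug scores into the model. If a stopper has an off-drug Day-30 score, it is already lower by the lost 6 points and pulls the Day-90 prediction down. With three visits and correlation 0.6, the coefficient of Day 30 given Day 15 is 0.6 × (1 − 0.6) / (1 − 0.6²) = 0.24 / 0.64 = 0.375. At m = 10% the excess becomes 0.60 × (1 − 0.375) = 0.375.

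A large-sample likelihood fit over Days 15, 30 and 90, with an effect of 6 at each visit, stopping after Day 15 and all effect then lost, gave:

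| Scores seen after stopping | 10% stop | 20% stop |
|---|---|---|
| None | 0.60 (m = 10%) | 1.21 (m = 20%) |
| All have Day 30, none Day 90 | 0.37 (m = 10%) | 0.76 (m = 20%) |
| Half have Days 30 and 90, half neither | 0.28 (m = 5%) | 0.54 (m = 10%) |
| All have Day 30, half Day 90 | 0.17 (m = 5%) | 0.32 (m = 10%) |

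Against 6m (0.30, 0.60 and 1.20 for m of 5%, 10% and 20%), every entry is at or below the bound, within simulation error of about 0.01. With no drug effect, or no loss of effect after stopping, the excess was zero within the same error.

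**5. Scale.** Ignoring the gain from earlier visits, the standard error of the difference is 20 × √(2/250) = 1.79, so the 95% half-width is 1.96 × 1.79 = 3.5 points. The bounds of 0.3, 0.6 and 0.9 are 0.17, 0.34 and 0.50 standard errors.

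**6. Which scores enter the MMRM.** SAP 7.5.2 does not say which of the two observed-case definitions in 6.6.3 applies. Table 6.7: 1 closes the Day-90 window a set number of days after treatment stop, which Table 6.1: 2 makes 7 for patient-reported outcomes. Read literally, a patient who stops at Day 40 has no Day-90 window, which conflicts with the intent of Protocol 7.2.1. The reduction in step 4 depends on that intent being followed.

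**The case against.** **The SAP follows the protocol.** Protocol 7.2.3 names KCCQ-TSS and prescribes the same implicit handling, and the protocol's cross-references send the primary and NT-proBNP analyses to 7.3 but not the MMRM. This stands. A reader might infer that the SAP breaches the protocol; it does not. The protocol's two sections pull in different directions, and the SAP took one of them. Section 4 of the SAP, which lists changes to the planned analysis, does not mention that the rule in 7.3 was narrowed.

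**An MMRM on all observed data is not in itself contrary to treatment policy.** This also stands. The weak point is missingness at random regardless of treatment status, and only for unobserved off-treatment scores: SAP 6.6.1 treats missing on-treatment scores as missing at random too.

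**Jump-to-placebo has its own error.** Protocol 4.1.4 lets patients resume drug until Visit 5, yet a footnote to SAP Table 6.6.1: 1 counts everything after any discontinuation as off-treatment. A resumed patient with a missing score would lose an effect that may be present. That is a reason to report both estimates.

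**The endpoint is exploratory and the shift is small.** True. But NT-proBNP is an exploratory secondary too, and it receives jump-to-placebo. No reason is given for treating KCCQ-TSS differently.

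**A sensitivity analysis may exist in withheld text.** Parts of both documents are missing, so its absence cannot be asserted. The main analysis in 7.5.2 is visible and clear.

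**Conclusion.** The inconsistency is real and worth correcting at low cost. The same unobserved off-treatment KCCQ-TSS score carries no drug effect in the win ratio and up to the full effect in the MMRM.

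A reader might conclude that the trial's KCCQ-TSS effect is overstated. The documents do not support that as a fact. It needs a true effect, loss of that effect on stopping, and stoppers with no Day-90 score, and no rate is given for the last. Under those conditions the excess is at most 6m: 0.3 to 0.9 points for m of 5% to 15%, and less where earlier off-drug scores are observed. The SAP states the loss-of-effect premise for its imputed analyses, not for the MMRM.

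Deaths should not be used to set m. Pairs involving a death are normally settled at tier 1, so the two analyses do not clash over those patients in the same way. The gap there is a different one: the MMRM implicitly gives a patient who died a Day-90 score, and the plan does not say whether that is intended.

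The primary test is not affected. Because the bias vanishes when there is no effect, this mechanism does not create a false positive.

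**What to change.** 1. In SAP 7.5.2, prespecify that the stated KCCQ-TSS model is also fitted to the 100 data sets completed under Section 6.6.1, with the Day-90 difference combined by Rubin's rules. Report it beside the MMRM, preferably as the main estimate, because it matches the declared estimand and tier 4.
2. Keep the MMRM on all observed on- and off-treatment scores, name the data definition used, and label it as assuming missing at random.
3. State how patients who die before Day 90 are handled in both analyses.
4. Reconcile Protocol 7.2.3 with 7.3, and record the resolution in SAP Section 4.

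The cost is a few sentences and one more model run on data sets already needed for the primary analysis. The preferred estimate would be slightly smaller if the drug works. No new data and no more patients are needed.
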